H_1 = The Humylub Ofteno® PF ophthalmic solution is inferior in efficacy to its comparators after 30 days of treatment, as it does not show a 35% decrease in the final OSDI test score from baseline in at least 30% of exposed patients.
$H_1: P_A - P_B > \delta$
Study design:
Phase IV non-inferiority, controlled, open-label, comparative, multicenter clinical trial.
Number of subjects (planned and analyzed):
Number of patients planned: 60 evaluable patients per arm. Total sample = 180 evaluable patients.
Diagnosis and main inclusion criteria:

 - Patients diagnosed with mild to moderate dry eye.
Selection criteria:
Inclusion criteria:

 - Can voluntarily give their signed informed consent. - Be able and willing to comply with scheduled visits, treatment plan, and other study procedures. - Be of legal age. - Women of childbearing potential must ensure the continuation (initiated ≥ 30 days prior to signing the informed consent form [ICF]) of the use of a hormonal contraceptive method or intrauterine device (IUD) during the study period. - Present a diagnosis of mild to moderate dry eye, defined by an OSDI rating ≥ 13 and one of the following: 
 o Corneal staining with more than 5 sites.

- Conjunctival staining with more than 9 sites.
- Tear film breaking time < 10 seconds.

Exclusion criteria:

[figure not shown]
- Women who are pregnant, breastfeeding, or planning to become pregnant within the study period.
- Have participated in another clinical research study ≤ 30 days prior to the screening visit.
- Have previously participated in this study.
- Have a CVAM of 20/200 or worse in one of the eyes.
- Present an ophthalmological diagnosis of:
 - Allergic, viral, or bacterial conjunctivitis.
 - Blefaritis anterior.
 - Parasitic infestations in any ocular structure or its appendages.
 - Unresolved eye trauma.
 - Healing diseases of the ocular surface.
 - Corneal or conjunctival ulcers.
 - Filamentous keratitis.
 - Neurotrophic keratitis.
 - Bullous keratopathy.
 - Neoplastic diseases on the ocular surface or adnexa.
 - Diseases with fibrovascular proliferations on the conjunctival and/or corneal surface.
 - Retinal and/or posterior segment diseases that require treatment or threaten visual prognosis.
 - Glaucoma.
 - Disorders of the eyelids that cause palpebral malpositions, limit the proper closing or opening of the eyelids, or are the cause of epiphora.

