3.3 Hypothesis

H_0 = The Humylub Ofteno® PF ophthalmic solution is not inferior in its efficacy compared to its comparators, after 30 days of treatment, presenting a 35% decrease in the final score of the OSDI test compared to its initial value in at least 30% of exposed patients.

$$H_0: P_A - P_B \leq \delta$$

H_1 = The Humylub Ofteno® PF ophthalmic solution is inferior in its efficacy compared to its comparators, after 30 days of treatment, as it does not present a 35% decrease in the final score of the OSDI test compared to its initial value in at least 30% of exposed patients.

$$H_1: P_A - P_B > \delta$$

4. Study design

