7.4.4 Definition of variables, methods and scales to be used for the measurement

Variable	Conceptual Definition	Operational Definition	Measurement Type	Normal value	Statistical test
OSDI Score	OSDI is a questionnaire designed to establish a severity and Classification of dry eye according to its symptoms.	The evaluator will apply the questionnaire to the subject and allow the subject to answer it calmly without any pressure and/or coercion. See annex 16.1 OSDI .	Continuous quantitative	Score: OSDI= $\frac{\sum \text{score}}{25}$ n answers answered	
 • ANOVA of repeated measures. • One-way ANOVA*
TRLNI	Measurement of tear rupture time using non-invasive methods based on the observation of the film's mirror reflection in a grating design or in the placid discs of the corneal topographers and their analysis using specialized software.	The TRLNI will be measured by means of the Oculus Keratograph 5M.	Discrete quantitative	>10s	
 • ANOVA of repeated measures. • One-way ANOVA*
Corneal and conjunctival staining with lysmine green	Detection of epithelial defects in the conjunctiva and cornea.	Direct observation with slit lamp, graduation on Oxford scale. See annex 16.2 Oxford scale .	Ordinal Qualitative	Degrees: The stain is presented in a series of panels (A-E). The points Stains range from 0-5 for each panel and from 0-15 for the exposed toral area of the conjunctiva and cornea.	
 • χ^2 (Chi-square) of Pearson or Fisher's Exacta • McNemar Test*

Corneal and conjunctival staining with fluorescein	
Detection of epithelial defects in the conjunctiva and cornea.
	
Direct observation with slit lamp, graduation on Oxford scale. See annex 16.2 Scale of Oxford.
	
Ordinal Qualitative
	
Degrees: The stain is presented in a series of panels (A-E). The points Stains range from 0-5 for each panel and from 0-15 for the exposed toral area of the conjunctiva and cornea.
	
 • χ^2 (Chi-square) of Pearson or Fisher's Exacta • McNemar Test*

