10.1.2 Data Interpretation

The Kolmogorov-Smirnov and Shapiro Wilk tests will be performed, as applicable, to determine if the distribution of the data is normal in the results obtained in each study group [56].

The results of the continuous quantitative variables will be presented in measures of central tendency: mean, standard deviation, standard error and/or ranges.

- Intra-group analysis: For equal variances, Tukey's POST-HOC test will be used, otherwise the Dunnett statistic will be used. One-way analysis of variance (one-way ANOVA) will be used when applicable.
- Intergroup analysis: Differences between groups will be analyzed using the Repeated Measures Analysis of Variance (ANOVA) test or the Student's t-statistic when applicable.

A non-inferiority margin (δ) of 10% will be used for the primary efficacy endpoint, based on the primary endpoint of the study. The level of difference to consider significance will be an alpha (α) of 0.05 or less.

The result of the nominal and ordinal qualitative variables will be presented in frequencies, proportions and/or percentages.

The statistical analysis to identify significant differences in the qualitative variables will be carried out by creating 2x2 contingency tables and will be carried out as follows:

- Intra-group difference: McNemar test. This is applied to 2x2 contingency tables with a dichotomous feature, with pairs of paired subjects, to determine if the marginal frequencies of row and column are equal (marginal homogeneity) [7].

- Difference between groups: Pearson's X² (Chi-square) test or Fisher's exact test at expected values less than 5.

The level of difference to consider significance will be an alpha (α) of 0.05 or less.

For the reporting of adverse events, all subjects who were randomly assigned to an intervention group after baseline (intention-to-treat population, ITT) will be considered.

The final report of the results will be shown in tables or graphs, as appropriate.

Variable Type	Variable	A1	B1	B2	C1	D1	D2	D3	D4	E1	E2
Background											
A1	Demographic	DT									
Basal											
B1	Medical History/Selection Criteria	DT									
B2	Comprehensive ophthalmological evaluation	DT				TB	T	T	T	TB	TB
Efficiency											
C1	OSDI	DB			B					TB	
Secondary efficacy outcome											
D1	TRLNI				DB	B				TB	
D2	Corneal and conjunctival stains (TVL and TF)		DT	DT			TB			TB	
D3	Conjunctival Hyperemia		DT	DT		TB				TB	
D4	Chemosis		DT	DT		TB				TB	
Safety											

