10.2.2 Justification for sample calculation

Sample size calculation was performed based on the results of the phase IV, multicenter, prospective, double-blind, randomized efficacy and safety clinical study of Humylub Ofteno® PF ophthalmic solution, versus Systane® Ultra and Systane® Ultra preservative free performed in subjects diagnosed with mild to moderate dry eye. The reduction in the mean score of the OSDI test was considered as the main efficacy variable, with a dosage of 1 drop QID. In this study, after one month of treatment, subjects assigned to Humylub Ofteno® PF had a decrease of -49.3% vs -41.3% for Systane Ultra and -48.3% for Systane Ultra PF, with respect to their initial mean values with no statistical differences between treatments ($p>0.05$) [57].

For the present protocol, it is expected that, after 3 days of treatment, 30% of subjects treated with Humylub Ofteno® PF will have a 35% decrease in OSDI score compared to their initial mean value.

The sample size was calculated using the equation for two proportions [58], considering a power of 80% (β), a significance level of 0.05 (α) and a margin of non-inferiority (δ) of 10% and based on the following working hypotheses:

$$H_0: P_A - P_B \leq \delta$$

$$H_1: P_A - P_B > \delta$$

Where, δ is the margin of non-inferiority and, the ratio between the sample size of the two groups is:

$$k = \frac{\eta A}{\eta B}$$

Equations

The calculation to estimate sample size and power was performed using an online tool and following the equations: [59]

$$n_A = kn_B \text{ y } n_B = \left(\frac{P_A(1 - P_A)}{k} + P_B(1 - P_B) \right) \left(\frac{z_{1-\alpha} + z_{1-\beta}}{p_A - p_B - \delta} \right)^2$$

$$1 - \beta = \Phi(z - z_{1-\alpha}) + \Phi(-z - z_{1-\alpha}) \text{ , } z = \frac{P_A - p_B - \delta}{\sqrt{\frac{P_A(1 - P_A)}{n_A} + \frac{P_B(1 - P_B)}{n_B}}}$$

$$k=nA/nB$$

Φ is the standard normal distribution function

Φ^{-1} is the standard normal quantile function

α is a Type I error,

β is the Type II error, which means that $1-\beta$ is the power, and

δ is the test margin.

According to the previous calculation, the result was 50 subjects, this calculation was increased by 20% considering possible losses (10 subjects). The total suggested sample size is 180 subjects (60 cases per arm), which will provide both eyes for the study.

11. Ethical considerations

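### The 80% power claim for 50 per arm has no stated comparator responder rate; at equal 30% rates the printed formula needs 260 per arm

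*Combined protocol and SAP*

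**What the plan says.** Section 10.2.2 uses the equation for two proportions, "considering a power of 80% (β), a significance level of 0.05 (α) and a margin of non-inferiority (δ) of 10" per cent. The printed equation has two responder rates: P_A for the test product and P_B for the comparator.

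- **P_A.** Section 10.2.2 expects that "after 3 days of treatment, 30% of subjects treated with Humylub Ofteno® PF will have a 35% decrease in OSDI score". Section 3.3 sets the time point at 30 days and words the rate differently: "presenting a 35% decrease in the final score of the OSDI test compared to its initial value in at least 30% of exposed patients".
- **P_B.** No responder rate for Hyabak or Lagricel is given in any section.
- **Earlier study.** Section 10.2.2 cites a previous phase IV trial in which, after one month, "subjects assigned to Humylub Ofteno® PF had a decrease of -49.3% vs -41.3% for Systane Ultra and -48.3% for Systane Ultra PF". These are reductions in mean OSDI score, and both controls are Systane products.
- **Result.** "According to the previous calculation, the result was 50 subjects, this calculation was increased by 20% considering possible losses (10 subjects"). The total is 180.
- **Analysis.** Section 7.4.4 classes the OSDI score as "Continuous quantitative". Section 10.1.2 says "Differences between groups will be analyzed using the Repeated Measures Analysis of Variance (ANOVA) test", or Student's t where applicable.
- **Evaluable target.** The synopsis has "60 evaluable patients per arm. Total sample = 180 evaluable patients", and section 10.2.1 also treats 60 per arm as evaluable. Section 10.1.4 requires 50.

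**The concern.** A two-proportion sample size cannot be checked without both proportions. One is missing, and the earlier-study figures cannot stand in for it: a percentage fall in a mean score is not a proportion of responders, and the controls were different products.

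The result also looks small. A 10-point margin with rates near 30% normally calls for hundreds per arm, not 50.

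The 80% figure is the only justification for the sample size, and section 5.6 relies on it again when it accepts losses below 20%. If the true power is far lower, failure to show non-inferiority would say little about the product. A reader also cannot tell whether 50 came from a sourced comparator rate or from an entry error.

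**Working it through.** **Inputs.** From section 10.2.2: delta = 0.10, alpha = 0.05, power 80%, P_A = 0.30. The equation uses z(1−alpha), so it is one-sided: 1.645 + 0.842 = 2.486. Equal arms give k = 1. P_B is not stated; P_B = 0.30 (equal efficacy) is an assumption here, and a range follows.

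**Formula.** n per arm = [P_A(1−P_A) + P_B(1−P_B)] × [2.486 / (P_A − P_B − delta)]².

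**The plan's own figure.** The 50 does not follow from the stated responder-rate inputs, because one input is absent.

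**Equal rates of 30%.** (0.21 + 0.21) × (2.486 / 0.10)² = 259.7, so 260 per arm. The sign of delta makes no difference at equal rates.

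**Power at the planned size.** z = 0.10 / √(0.42/n); one-sided power = Φ(z − 1.645).

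- n = 50: z = 1.091, power 29.0%.
- n = 60: z = 1.195, power 32.6%.
- The protocol's own two-term power formula gives 29.3% and 32.9%.

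**Other equal rates.**

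| Common rate | n per arm for 80% | Power at 50 | Power at 60 |
|---|---|---|---|
| 10% | 112 | 51% | 57% |
| 20% | 198 | 35% | 39% |
| 30% | 260 | 29% | 33% |
| 40% | 297 | 27% | 30% |
| 50% | 310 | 26% | 29% |

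P(1−P) is symmetric about 50%, so 60% to 90% repeat these rows in reverse (70%: 260; 90%: 112). Below 50%, 50 per arm reaches 80% power only if the common rate is about 4.2% or lower.

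**Unequal rates, P_A = 30%.** These rows use delta = −0.10, the usual non-inferiority direction, not the sign as printed.

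| P_B | n per arm for 80% | Power at 50 | Power at 60 |
|---|---|---|---|
| 20% | 58 | 75% | 82% |
| 25% | 110 | 51% | 58% |
| 30% | 260 | 29% | 33% |
| 35% | 1082 | 13% | 14% |

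**What would give 50.** With P_A = 30% and delta = −0.10, n = 50 is met at P_B = 18.8%, an advantage of 11.2 points. The advantage needed is 8.1 points at P_A = 20%, 13.2 at 40% and 14.4 at 50%. With delta = +0.10 as printed, n = 50 is met at P_B = 2.9% or about 43.7%. The inputs actually used therefore cannot be inferred from the result. At equal 30% rates, 50 per arm would need a margin of about 22.8 points.

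**Both eyes.** Counting both eyes as independent units does not close the gap: 100 eyes per arm gives 46% and 120 gives 52%.

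**Loss allowance (minor).** 50 × 1.2 = 60 reproduces. But 60 × 0.8 = 48, and 50 evaluable after a 20% loss needs 50 / 0.8 = 62.5, so 63. At equal 30% rates, power is 28.2% at 48 against 29.0% at 50.

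**The case against.** **Equal 30% rates are an assumption, not a design input.** Section 3.3 reads as a floor, and the earlier study's mean reductions of 41% to 49% exceed the 35% responder threshold, so rates above 50% are conceivable. This is fair, but by symmetry higher common rates do not help: power at 50 to 60 per arm never exceeds about 57% for any common rate from 10% to 90%.

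**The unequal-rate figures reverse the printed sign of delta.** With +0.10, P_B = 25% needs 984 per arm and P_B = 35% needs 121, and P_B = 20% has no solution. This stands as a labelling point, so those rows are marked. The equal-rate result does not depend on the sign.

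**The 50 can be reached from printed percentages.** Entering 0.35 and 0.493 with delta = +0.10 returns 49.99. That pair was found by searching. The first value is the decrease threshold and the second is the earlier mean reduction on Humylub; neither is stated as a responder rate. It shows that an entry error is possible, and does not support 80% power.

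**The power figures do not describe the planned test.** This stands. The primary variable is a continuous score with no stated SD, so it is not established that the ANOVA or t test is underpowered. But 80% was derived from the responder model, and no other basis is given.

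**The loss arithmetic is peripheral.** Agreed. Section 10.1.4 allows replacement when losses exceed 20%, and the effect is under one point of power.

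**Conclusion.** The concern holds and must be fixed. The 80% power claim rests on a comparator responder rate that the protocol does not state, and 50 per arm does not follow from the responder rates it does state. Assuming equal true rates of 30%, a 10-point margin and one-sided alpha 0.05, the printed formula needs 260 per arm, and 50 to 60 per arm gives about 29% to 33% power. On that model, a trial of equally effective products would miss non-inferiority about two times in three.

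The 80% would be justified only by an unstated advantage for Humylub: with P_A = 30% and delta = −0.10, P_B about 19% or lower.

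All figures are for one pairwise comparison in the responder model. The primary objective names two comparators, and the power to succeed against both would be lower. The power of the planned analysis of the OSDI score cannot be assessed from the documents.

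**What to change.** In section 10.2.2:

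1. State P_A with its time point, reconciling the 3 days there with the 30 days in section 3.3.
2. State P_B for Hyabak and for Lagricel, each with its source.
3. State the signed margin that was entered, and rerun the formula.
4. Unless a sourced P_B supports 80%, replace the claim with the power that 50 to 60 per arm delivers over a range of P_B that includes equal rates (about 29% to 33% at 30% versus 30%).
5. Say that these figures refer to the responder rate and not to the ANOVA or t test on the OSDI score.

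Minor: use one evaluable target in the synopsis, 10.1.4 and 10.2.1, and correct the loss allowance (63 enrolled for 50 evaluable at 20% loss).

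The cost is protocol and SAP wording and one rerun of the formula. Restating the power needs no extra patients, but it does not raise the power either. The downside is a less favourable stated power if no sourced P_B supports 80%.

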10.1.4 Deviations from the statistical analysis plan

According to the calculation of the sample size to meet the objective of the study, 50 evaluable patients are required per arm. If this number is not met due to a loss of patients greater than 20% contemplated in this protocol (loss of follow-up or withdrawal of ICF), the sponsor may replace these patients.

The results obtained from the replaced patients will continue to be used for safety analysis and will be part of the ITT.

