10.2 Sample Size Calculation

10.2.1 N Calculated

Number of planned patients: 60 evaluable patients (both eyes) per arm

Total N = 180 patients

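### The loss allowance in section 10.2.2 (50 raised to 60 per arm) covers 16.7% of randomised patients, not the 20% tolerance that section 5.6 and, on its natural reading, section 10.1.4 rely on

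*Combined protocol and SAP*

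**What the plan says.** Section 10.2.2 gives the base figure and the allowance: "the result was 50 subjects, this calculation was increased by 20% considering possible losses (10 subjects"). It concludes: "The total suggested sample size is 180 subjects (60 cases per arm").

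Section 10.1.4 sets the number needed at analysis, "50 evaluable patients are required per arm", and makes replacement conditional: "If this number is not met due to a loss of patients greater than 20% contemplated in this protocol". It names loss to follow-up and withdrawal of consent as the losses meant, and says that the sponsor may then replace the patients.

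Section 5.6 defines loss to follow-up among randomised patients, as those whose final evaluation could not be completed. It states that a loss below 20% does not threaten the validity of the results, and refers to the sample size calculation in section 10.2 for support.

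Section 10.2.1 describes the 60 differently: "Number of planned patients: 60 evaluable patients (both eyes) per arm". The synopsis also labels the 60 per arm, and the 180 in total, as evaluable.

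Section 10.1.5 restricts the analysis for the study objective to patients with at least 65% adherence by bottle weight and at least 80% by diary.

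**The concern.** To keep 50 patients after losing a fraction d of those randomised, one divides 50 by (1 - d). Section 10.2.2 multiplies by (1 + d), which gives a smaller number. The plan then uses 20% twice more: as the loss that section 5.6 calls harmless, and as the threshold in section 10.1.4 above which patients may be replaced. If both percentages refer to randomised patients, the allowance runs out before either threshold is reached. An arm could then fall below the required 50 while the condition for replacement is still unmet. Calling both 50 and 60 evaluable makes it harder to see which number the percentage applies to.

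**Working it through.** **Inputs.** Base size 50 per arm, allowance 20% (10 patients), planned size 60 per arm and 180 in total (10.2.2). Required evaluable number 50 per arm, replacement condition a loss above 20% (10.1.4). Loss described as harmless: below 20% (5.6).

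**Reproducing the plan's figure.** 50 x (1 + 0.20) = 60 per arm, and 3 x 60 = 180. The stated numbers follow exactly from adding 20%.

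**What 60 covers.** 60 x (1 - 0.20) = 48, two short of 50. The largest loss that leaves 50 is 60 - 50 = 10, and 10/60 = 16.7%.

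**What 20% would need.** 50/(1 - 0.20) = 62.5, so 63 per arm (63 x 0.8 = 50.4, whereas 62 x 0.8 = 49.6). The total would be 3 x 63 = 189, which is 9 more than planned.

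**The replacement condition, taking 20% as a share of the 60 randomised in an arm.**

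| Lost of 60 | Loss | Remaining | Below 50? | Above 20%? |
|---|---|---|---|---|
| 10 | 16.7% | 50 | no | no |
| 11 | 18.3% | 49 | yes | no |
| 12 | 20.0% | 48 | yes | no |
| 13 | 21.7% | 47 | yes | yes |

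At 11 and 12 losses the required number is missed and the condition is not met. Section 5.6 uses a strict limit of less than 20%, so only the row with 11 losses contradicts it; 12 losses is exactly 20%.

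**Effect on power.** Assume that 50 per arm gives exactly 80%. Then power at n is Φ[(z₁₋α + z₀.₈₀) x √(n/50) - z₁₋α].

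- One-sided α = 0.05, as the z₁₋α in the plan's formula implies: 79.3% at 49 and 78.6% at 48.
- One-sided α = 0.025, for comparison: 79.2% at 49 and 78.4% at 48.

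The loss is therefore at most about 1.5 percentage points (80 - 78.6 = 1.4; 80 - 78.4 = 1.6).

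**Non-adherence.** Patients excluded under 10.1.5 also reduce the analysed number. As an illustration, 5 losses (5/60 = 8.3%) and 6 non-adherent patients leave 60 - 5 - 6 = 49. Section 10.2.2 attributes the 10 extra patients to losses and states no separate allowance for these exclusions.

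**The case against.** The strongest reply concerns the denominator. Section 10.2.2 equates 20% with 10 patients, so its 20% is taken on 50. Section 10.1.4 refers to the 20% contemplated in the protocol, which may point back to that allowance. On that reading the condition is more than 10 losses: 11 losses leave 49, the number is missed, replacement is open, and there is no gap. This reading is possible for 10.1.4 and 10.2.2, and no section states the denominator or says whether the 20% is counted per arm or overall. It does not fit section 5.6, which defines loss among randomised patients and so reads naturally as a percentage of them. The 16.7% figure and the double use of the word evaluable stand on either reading.

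A second reply is that the effect is minor. That is right: one or two patients per arm.

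Three stronger inferences are tempting, and the documents do not support them.

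- A reader might infer that the two evaluable figures lead to conflicting replacement decisions. No replacement rule is attached to the 60; section 10.1.4 ties replacement to 50 alone. The conflict is one of labelling.
- A reader might infer that the plan declares no action necessary at or below 20%. Section 10.1.4 is permissive: it says when the sponsor may replace, and gives no instruction for smaller losses.
- A reader might infer that patients excluded for non-adherence must be replaced. Refilling an adherence-selected set in an open-label trial is a debatable trade-off, and not replacing them is a defensible choice.

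**Conclusion.** The point holds, at modest size. Sixty randomised per arm tolerates a loss of 10 (16.7%), not 20%. The statement in section 5.6 that a loss below 20% is harmless is wrong on the plan's own numbers at 11 losses per arm. If the 20% in section 10.1.4 is also a share of randomised patients in an arm, then 11 or 12 losses leave 49 or 48 evaluable patients without meeting the replacement condition. That part depends on a denominator that the plan leaves unstated.

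The cost is one or two patients per arm and about 1.5 percentage points of power, assuming that 50 gives 80%. This is not evidence that the trial is materially underpowered. Whether 50 is the correct output of the formula is a separate question, and correcting the allowance would not settle it.

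**What to change.** 1. In sections 5.6, 10.1.4 and 10.2.2, state the tolerated loss as 10 of 60 randomised patients per arm (16.7%). Alternatively, keep 20% and say that it leaves 48 per arm.
2. In section 10.1.4, replace the percentage condition with a count: fewer than 50 evaluable patients in an arm, that is, more than 10 losses. This removes the doubt about the denominator and about per-arm or overall counting.
3. Use randomised for the 60 and evaluable for the 50 in the synopsis and sections 10.1.4, 10.2.1 and 10.2.2.
4. Add a sentence noting that exclusions under section 10.1.5 draw on the same 10 patients. It need not require their replacement.

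These are wording changes and one restated percentage, with no increase in the planned 180. Only if the sponsor wants true cover for a 20% loss would the plan rise to 63 per arm, 189 in total. If the base of 50 is ever recalculated, the allowance should be applied by dividing by (1 - d), so that the same slip does not carry over.
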